3.6 Stratification, Randomization, and Blinding

For Stage 2 randomization, participants will be stratified by screening gene expression signature:

- Group 1: high interferon and high inflammation
- Group 2: low inflammation and high B Cells (interferon can be high or low)
- Group 3: other profiles not included in groups 1 or 2
- Group 4: gene expression signature results unavailable (e.g. due to shipping or laboratory error)

For Stage 3 re-randomization, participants will be stratified by the Stage 2 treatment assignment: MMF vs Placebo MMF along with whether or not a long-acting corticosteroid injection was given at the time of Stage 2 treatment failure.

The randomization will be performed by the Division of Allergy, Immunology, and Transplantation (DAIT) Statistical and Clinical Coordinating Center (SCCC). Blinding will be maintained for all study participants and trial personnel throughout the study, except for the study site pharmacist. Treatment assignments will be centrally randomized and communicated to the unblinded study site pharmacist. The investigators, clinic personnel, and participants will not be informed regarding the intervention assignment until the study is unblinded. Laboratories performing assays for this protocol will be blinded to the identity and group assignment of biological materials to be studied.

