13.4 Analysis Plan

13.4.1 Analysis Populations

13.4.1.1 Stage 2 Analysis Populations

Modified Intent to Treat Population:

The modified Intent-to-Treat population (mITT) will consist of all Stage 2 randomized participants who received at least one dose of MMF or MMF placebo. The mITT population will be used for all Stage 2 efficacy analyses and will include participants under the treatment to which they were randomized, regardless of compliance with assigned treatment.

Per Protocol Populations:

Two per protocol (PP) populations will be defined for Stage 2 analyses.

The PP1 population will consist of mITT participants who:

- Have either completed the Stage 2 Week 24 visit without experiencing a Stage 2 failure or have experienced a treatment failure on or prior to Stage 2 Week 24;
- Have $\geq 80\%$ compliance with MMF or MMF placebo administration from randomization through the Stage 2 Week 24 visit or until treatment failure (whichever comes first), where compliance is assessed by numbers of capsules of study product returned to the site;
- Have no protocol violations or ineligible entry criteria deemed likely to affect the efficacy outcomes of interest either through Week 24 of Stage 2 or treatment failure (whichever comes first).

The PP2 population will consist of mITT participants who:

- Have either completed the Stage 2 Week 48 visit without experiencing a Stage 2 failure or have experienced a treatment failure on or prior to Stage 2 Week 48;
- Have $\geq 80\%$ compliance with MMF or MMF placebo administration from randomization through the Stage 2 Week 48 visit or until treatment failure (whichever comes first), where compliance is assessed by numbers of capsules of study product returned to the site;
- Have no protocol violations or ineligible entry criteria deemed likely to affect the efficacy outcomes of interest either through Week 48 of Stage 2 or treatment failure.

A blinded data review panel will evaluate deviations from the protocol including, for example, violations of entry criteria, departures from assigned treatment regimen, modifications of concurrent therapy, failure to complete study visits, or administration of study procedures outside the specified visit windows to determine if occurrence of these deviations should exclude participants from the PP1 or PP2 population.

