13.4.2 Primary Analysis of Primary Endpoint

The primary endpoint is the cumulative incidence of treatment failure at or before the Stage 2 Week 24 visit. Time to treatment failure is defined as the interval from the day of Stage 2 randomization until the day of treatment failure (as defined in Section 3.2, Primary Endpoint). Participants who withdraw from the study early without evidence of treatment failure will be censored at day of the last assessment they were determined to be failure-free. The risk of treatment failure over the period of Stage 2 randomization through 24 weeks of follow-up will be presented graphically using Kaplan-Meier product limit estimates of the survival function in subgroups defined by treatment arm and by immunologically-homogenous subsets. The Kaplan-Meier estimates of event-free survival and confidence intervals using Greenwood's formula for standard error will be reported by subgroup at Stage 2 Week 24. The primary analysis will be a stratified two-sample test of the cumulative incidence of treatment failure at Stage 2 Week 24 using a 2-sided $\alpha=0.05$.

The ultimate goal of Stage 2 is to evaluate the potential effectiveness of MMF within the 7 previously-identified immunologically-homogeneous clusters for lupus. Regardless of the outcome of the stratified test for the pooled analysis, within-cluster landmark two-sample tests will be performed for comparisons of the cumulative incidence of treatment failure at Stage 2 Week 24 for each cluster. Due to the limited samples sizes anticipated in each immunologically-defined subgroup, no correction for multiple comparisons will be made, and p-values of < 0.10 will be considered notable findings but will be interpreted with caution given the high probability of a family-wise error with multiple comparisons under a strong null hypothesis of no treatment benefit.

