13.4.5 Analyses of Secondary Efficacy Endpoints

The key secondary efficacy endpoint is clinical response at Stage 2 Week 24, defined by the BICLA (see Section 3.3.1, Efficacy Endpoints). A Fisher's exact test (2-sided $\alpha=0.05$) will be performed to test the hypothesis that there is no difference in the proportion of responders between treatment groups. This analysis will also be repeated at Stage 3 Week 24. An additional supportive Stage 3 analysis will use the most recent assessment before the Stage 3 Day 0 visit as the reference (see Section 3.5.3, BILAG-based Combined Lupus Assessment (BICLA)).

For Stage 3, the cumulative incidence of participants who experience a treatment failure in Stage 3 will be evaluated. The primary analysis will be repeated considering treatment failures occurring during the time period from Stage 3 re-randomization through Stage 3 Week 24.

Time to treatment failure will also be evaluated in Stage 3, where the Kaplan-Meier estimation and log-rank tests from the supportive analysis of the primary analysis will be repeated for the time period from Stage 3 re-randomization through Stage 3 Week 24.

Given the unknown samples sizes and subgroups defined by Stage 2 treatment assignment, all inferential analyses for Stage 3 are considered supportive; p-values for test of differences among groups will be presented without adjustment for multiple comparisons, and p-values of < 0.10 will be considered notable findings.

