Although the number per cluster will be random, if the 7 clusters are evenly distributed in the lupus population, then the number achieved for any given cluster will likely include 11 to 24 individuals (i.e. $> 90\%$ chance) or approximately 5 to 12 per arm. Hence, we are likely to have adequately powered comparisons for at least some clusters.

For Stage 3, we anticipate that at least 48 (80%) among those randomized to placebo in Stage 2 and approximately 36 (60%) among those randomized to MMF in Stage 2 will be eligible for re-randomization to MMF or MMF plus voclosporin. For Stage 3 analyses, we will have 4 groups defined by the cross-classification of Stage 2 and Stage 3 treatment assignments, as follows:

Stage 2 Randomization

Stage 3 Re-randomization	MMF	Placebo MMF
MMF + voclosporin	n_{MMF_Combo} (~18)	$n_{placebo_Combo}$ (~24)
MMF + placebo voclosporin	n_{MMF_MMF} (~18)	$n_{placebo_MMF}$ (~24)

Stage 3 is intended to explore baseline (pre-re-randomization) gene expression patterns and their associations with response (or non-response) to MMF and MMF plus voclosporin, and to describe differences in those associations between the 2 arms. Gene expression patterns may include immunologically-homogeneous clusters defined at screening, gene expression at the Stage 2 Day 0 Randomization Visit, or differential expression observed during the Stage 2 treatment period. Among those randomized to placebo in Stage 2, if we re-randomize 24 to MMF, we anticipate 8-12 responders (i.e. 35-50% who have not failed by Stage 2 Week 24) and 12-16 non-responders on which to evaluate baseline gene expression patterns. In the MMF plus voclosporin arm, the number of responders is expected to be at least as high as MMF alone. Stage 3 is exploratory and not powered to test a pre-specified hypothesis.

14 Identification and Access to Source Data

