17.1 Statement of Compliance

This clinical study will be conducted using good clinical practice (GCP), as delineated in Guidance for Industry: E6 Good Clinical Practice Consolidated Guidance, and according to the criteria specified in this study protocol. Before study initiation, the protocol and the informed consent documents will be reviewed and approved by the IRB. Any amendments to the protocol or to the consent materials will also be approved by the IRB before they are implemented.

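### The key secondary BICLA comparison uses an unstratified Fisher's exact test, which gives up about 7 points of power for a 20-point difference at 60 per arm; the loss is small if the effect is large

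*Combined protocol and SAP*

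**What the plan says.** Section 13.4.5 states: "The key secondary efficacy endpoint is clinical response at Stage 2 Week 24, defined by the BICLA". It then specifies a two-sided Fisher's exact test at 0.05, which "will be performed to test the hypothesis that there is no difference in the proportion of responders between treatment groups", and repeats the analysis at Stage 3 Week 24. It names no stratification factor and no effect estimate.

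Elsewhere the plan does use strata:

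- Section 3.6: "For Stage 2 randomization, participants will be stratified by screening gene expression signature". There are four groups, the fourth being participants whose signature result is unavailable.
- Section 3.6, Stage 3: re-randomisation is stratified by Stage 2 arm "along with whether or not a long-acting corticosteroid injection was given at the time of Stage 2 treatment failure".
- Section 13.4.2: "The primary analysis will be a stratified two-sample test of the cumulative incidence of treatment failure at Stage 2 Week 24". The strata are not named there.
- Section 13.4.3: the supportive log-rank test is also stratified.

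On who is analysed, section 13.4.1.1 says "The mITT population will be used for all Stage 2 efficacy analyses". Neither section 3.5.3 (the BICLA definition) nor section 13.4.5 says how a participant who fails before Week 24 is scored. The documents give no BICLA response rate and no power for this endpoint.

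**The concern.** The key secondary test departs from the stratified approach used for the primary comparison, and it uses a test known to run well below its nominal level at this sample size. Both features cost power.

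The size of the cost depends on three things the documents leave open: the BICLA rates, whether the signature groups predict response, and how many participants per arm have an outcome. For differences of the size the trial plans around, the loss could decide whether the key secondary result supports the primary one. Stage 3 has the same mismatch, but section 13.4.5 calls all Stage 3 inference supportive, so it matters less there.

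**Working it through.** **Inputs.** From section 13.7: 120 participants randomised 1:1, so 60 per arm, with planning rates for the primary endpoint of 15% (placebo) and 35% (MMF) free of failure at Week 24. From section 13.4.5: two-sided 0.05. Assumed: BICLA rates, stratum sizes (20/20/20 per arm) and an outcome for all 60 per arm.

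**Reproducing the plan's own figure.** Section 13.7 uses an unpooled Z-test with binomial enumeration. Summing Bin(x; 60, p1) × Bin(y; 60, p0) over all 61 × 61 outcomes with |Z| > 1.96 gives 73.8% at 15% v 35% (stated: 74%) and 80.7% at 15% v 37% (stated: at least 80%). Both agree.

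**Tests compared.** The same enumeration was run with two rejection rules:

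- Fisher: reject if the sum of the hypergeometric probabilities no larger than the observed one is ≤ 0.05.
- CMH without continuity correction: reject if [Σ(x_k − n1k·m_k/N_k)]² / Σ[n1k·n0k·m_k(N_k − m_k)/(N_k²(N_k − 1))] > 3.84, where in stratum k, x_k is responders on MMF, n1k and n0k are the arm sizes, m_k is all responders and N_k is everyone.

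**Exact power, 60 per arm, CMH with one stratum.** This isolates the effect of replacing Fisher's test.

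| Placebo v MMF | Fisher | CMH | Gain (points) |
|---|---|---|---|
| 10 v 25% | 49.4% | 58.0% | 8.6 |
| 10 v 30% | 73.0% | 79.4% | 6.4 |
| 15 v 35% | 65.2% | 72.2% | 7.0 |
| 20 v 40% | 60.0% | 67.1% | 7.1 |
| 30 v 50% | 54.2% | 61.6% | 7.4 |
| 10 v 35% | 88.7% | 92.2% | 3.5 |
| 15 v 40% | 83.4% | 87.8% | 4.4 |
| 15 v 45% | 93.8% | 95.8% | 2.0 |
| 15 v 50% | 98.2% | 98.9% | 0.7 |
| 10 v 50% | 99.8% | 99.9% | 0.1 |

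**Why Fisher loses.** Its exact size at common rates of 10, 15, 20, 25, 30 and 35% is 2.2, 2.7, 2.8, 3.0, 3.1 and 3.1%. CMH with a continuity correction has 65.2% power at 15% v 35%, the same as Fisher, so the correction must be left off.

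**What the strata add.** Simulation, 200,000 trials per scenario, average rates close to 15% v 35%:

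| Strata | Fisher | CMH, unstratified | CMH, stratified | Stratified minus Fisher |
|---|---|---|---|---|
| Not prognostic | 65.1% | 72.1% | 72.6% | 7.5 |
| Mild (8, 15, 22% v 25, 35, 45%) | 65.4% | 72.5% | 73.9% | 8.5 |
| Strong (5, 10, 30% v 20, 30, 55%) | 65.8% | 73.0% | 76.9% | 11.1 |

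Stratification itself therefore adds 72.6 − 72.1 = 0.5, 73.9 − 72.5 = 1.4 and 76.9 − 73.0 = 3.9 points. At 30% v 50% the total gain is 7.4, 8.0 and 12.3 points.

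**In participants.** Fisher needs about 68–69 per arm to reach 72.6–73.3% power at 15% v 35%. That is 2 × 8 to 2 × 9, or 16–18 more people.

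**Fewer evaluable.** At 15% v 35%, Fisher v unstratified CMH is 59.9% v 68.2% with 54 per arm and 54.2% v 62.7% with 48.

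**If Stage 2 failures were left out.** Section 13.7 expects at least 48 placebo and about 36 MMF participants to move to Stage 3. That leaves about 60 − 48 = 12 v 60 − 36 = 24. For 20-point differences from 40, 50 or 60%, Fisher has 14–18% power and CMH 19–24%.

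**Stage 3 BICLA.** With 24 + 18 per arm (section 13.7) and an assumed 25-point effect, stratified CMH gains 3.7–10.4 points at 0.05 and 7.2–11.1 at 0.10.

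**The case against.** The strongest counter-argument is that little of this loss comes from ignoring the strata. That is correct when the strata are not prognostic: a plain unstratified Pearson chi-square reaches 73.5% at 15% v 35%, slightly above stratified CMH. The case for stratifying rests on matching the randomisation and the primary test, and on the extra gain if the signature groups predict response. The documents do not show that they do.

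Fisher's test is also valid, and preferring guaranteed size control is a defensible choice in a small Phase 2 trial with a possibly tiny fourth stratum. CMH is asymptotic. Its simulated size was 4.8–5.1% in the three-stratum scenarios examined, but it reaches about 5.5–5.6% at a common rate of 50%. If failures count as non-responders, that rate is far above what the plan implies, because BICLA response could then not exceed failure-free survival, planned at 15% or less on placebo. By the same logic, the 20 v 40% and 30 v 50% rows are sensitivity cases. For placebo rates of 5–15% the gain is still about 5–7.5 points (5.2 at 5% v 25%).

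Finally, no power is claimed for BICLA, no gatekeeping rule depends on this p-value, and Stage 3 is explicitly not powered. These points limit the importance of the finding. They do not supply a reason for the chosen test.

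**Conclusion.** The concern holds. For a true 20-point difference at 60 per arm, the planned test gives up about 7 points of power against an uncorrected CMH test on the randomisation strata, and about 11–12 points if the strata are strongly prognostic. The loss largely disappears for differences of 35 points or more.

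This rests on assumed BICLA rates and on all 60 per arm having an outcome. The mITT rule points towards the second assumption, but the BICLA sections do not state it. If failures were excluded, both tests would be badly underpowered and that would be the larger problem. There is no bias and no inflation of type I error. The change is worth making but not essential to the trial's validity, and the Stage 3 part is secondary.

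**What to change.** In section 13.4.5, and in matching SAP text:

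1. Replace Fisher's test for Stage 2 BICLA with a two-sided CMH test **without continuity correction**, stratified by the section 3.6 signature groups.
2. Report the Mantel-Haenszel risk difference with its 95% CI.
3. Fix one sparse-stratum rule, based on counts and not outcomes: if a stratum has nobody in one arm, pool it with the smallest other stratum; otherwise keep all strata.
4. For the supportive Stage 3 BICLA analysis, use the same test stratified by Stage 2 arm and injection at failure, pooling injection levels within a Stage 2 arm under the same rule.

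The same text should state how Stage 2 failures before Week 24 are scored for BICLA, because the effective sample size depends on it.

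**Cost.** A short amendment before unblinding, with no change to sample size, visits or data. It needs IRB approval, since section 17.1 says "Any amendments to the protocol or to the consent materials will also be approved by the IRB before they are implemented". The price is asymptotic rather than guaranteed size control. Simulated size was 4.8–5.0% with a fourth group of 3 per arm, and 4.9–5.0% under the pooling rule with a fourth group of 1 to 6 people in total, where power at 15% v 35% was 72.5–72.9%. In Stage 3, with no-injection cells of 3 and 2 per arm, it was 4.9–5.2% at 0.05 and 9.6–10.1% at 0.10. Pooling an unavailable-signature group with another group is somewhat arbitrary, but without it a stratum with one empty arm would contribute nothing.

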1.2.2 Rationale for Withdrawal of Background Medication

Since participants will be receiving a proven effective treatment for their immediate symptoms through steroid injections, this mitigates concerns that reduction of background treatments as early as the Screening Visit might precipitate a flare. Indeed, since all patients will be entered with active disease, the treatments being withdrawn will not be effective at that time point by definition. Safety is improved by allowing a washout of potentially interacting immune suppressants prior to starting the investigational treatment. Furthermore, simplification of background treatment early in the study will improve interpretability of both clinical and biomarker data, providing a valuable clarity for evaluation of the study treatment(s). In particular, the evaluation of MMF as a single agent will be facilitated by allowing it to exert its effects as a single agent from the start of administration.

Substitution of an ineffective treatment with a known, almost universally effective treatment (corticosteroid) is consistent with standard of care. The actual withdrawal of background treatment per se begins as a gradual decline in steroid levels over time. The earliest flares may start within a month, indicating that sufficient steroid dose was likely not given during the withdrawal phase. In the rare situations this does not ameliorate disease activity sufficiently for a participant to safely enter the trial, the participant will be taken off study, and they will be treated with whatever is appropriate at that time. Most flares in studies of this design occur after 2 or 3 months. This allows time to distinguish an effective treatment from placebo. As a flare becomes apparent, the participant becomes a non-responder in that part of the protocol and will also be immediately treated. Because of this, the trial design is in some ways easier to tolerate than some alternative protocols where participants who do not feel well must drop out or wait many weeks for treatment.

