1.2.3 Rationale for the Current Two-Part Protocol Design

The two parts of this protocol are designed to:

- Test the clinical and immunologic effects of MMF, compared to placebo in phenotypic clusters of participants with SLE. This first part of the trial (Stage 2) is expected to identify molecular clusters associated with clinical success or failure of MMF treatment.
- Test the clinical and immunologic effects of adding voclosporin (or not) for those participants who do not respond to MMF alone. Compare MMF vs MMF + voclosporin in a subset of non-responders who received placebo in the first part (Stage 2) of the trial. If one or more clusters of participants who have not responded to MMF alone can be identified by immunophenotypes, either at baseline or after receiving MMF, the question of whether all of these or only certain subsets are candidates for voclosporin can be addressed in an exploratory way. The study is likely underpowered to fully confirm cluster association with response (non-response) in this second part of the trial (Stage 3). The observations obtained may provide important hypotheses for further testing.

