13.4.6 Analyses of Exploratory Endpoints

Details of the exploratory analysis of clinical endpoints will be outlined in the SAP. For mechanistic endpoints, exploratory analyses will be conducted separately for subgroups allocated to each Stage 2 treatment arm because participants entering Stage 3 from the different treatment arms are not comparable at the point of re-randomization. Mechanistic plans are to explore baseline (pre-re-randomization) gene expression and protein level patterns among those who respond (or do not respond) to MMF and MMF plus voclosporin, and to describe differences between the 2 arms. Response will be defined using BICLA at 24 weeks post re-randomization.

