13.7 Sample Size Considerations

The goal of Stage 2 of the study is to evaluate the potential effectiveness of MMF within previously-identified immunologically-homogeneous clusters of lupus patients. To place these cluster comparisons in the context of a successful trial, target enrollment is based on power to show superiority of MMF over placebo in a pooled lupus population.

In previous studies using BOLD designs in lupus populations [22, 93, 94] where long-acting corticosteroids were administered during the treatment withdrawal stage, survival free-from-failure at 6 months in untreated or placebo-treated participants ranged from 5-20% [25]. These studies included participants with a range of disease activity, had differing rules on implementation of background steroids and different definitions for treatment failure. By limiting steroids and carefully adhering to entry criteria to recruit an appropriate population with active lupus disease activity, and by defining treatment failure to include individuals who receive rescue medications post-randomization or who withdraw from treatment prematurely, a placebo survival at 24 weeks of 15% or less should be achievable. In the MMF arm, a minimum clinically meaningful improvement would be 35% survival at 24 weeks.

A study design with 120 participants randomized 1:1 to placebo or MMF will have between 74% to \geq 95% power if placebo survival at Stage 2 Week 24 ranges from 15% to 10% and MMF survival at Stage 2 Week 24 ranges from 35% to 50% (2-sided, $\alpha=0.05$); power is \geq 80% when MMF survival at Stage 2 Week 24 is at least 37%. Power for a two-sample landmark analysis was computed for a Z-Test with unpooled variance using binomial enumeration.

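### The Stage 3 clinical tests are not specified within, or stratified by, Stage 2 arm, so none of them isolates the effect of adding voclosporin after failure on MMF

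*Combined protocol and SAP*

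**What the plan says.** Section 1.2.3 gives the second part of the trial two clinical aims. The first is "Test the clinical and immunologic effects of adding voclosporin (or not) for those participants who do not respond to MMF alone". The second is "Compare MMF vs MMF + voclosporin in a subset of non-responders who received placebo in the first part (Stage 2) of the trial".

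Section 3.6 builds that distinction into the design: "For Stage 3 re-randomization, participants will be stratified by the Stage 2 treatment assignment", together with whether a steroid injection was given at Stage 2 failure.

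Section 13.4.5 specifies the Stage 3 clinical tests by reference to Stage 2:

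- BICLA response: after describing Fisher's exact test for Stage 2 Week 24, it says "This analysis will also be repeated at Stage 3 Week 24".
- Treatment failure: "The primary analysis will be repeated considering treatment failures occurring during the time period from Stage 3 re-randomization through Stage 3 Week 24".
- Time to failure: the Kaplan-Meier and log-rank methods of the supportive Stage 2 analysis are repeated.

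The section names no Stage 3 strata for any of these. It refers to subgroups by Stage 2 assignment only when explaining why Stage 3 inference is supportive. P-values below 0.10 are still to be called notable.

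Section 13.4.6 separates the Stage 2 arms because "participants entering Stage 3 from the different treatment arms are not comparable at the point of re-randomization", but applies this to mechanistic endpoints only. Section 13.7 lists four Stage 3 groups (Stage 2 arm by Stage 3 arm) and assigns no clinical test to them.

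**The concern.** The two aims concern different people. Those who failed on MMF continue it and either add voclosporin or do not. Those who failed on placebo start MMF, with or without voclosporin. The effect of voclosporin may differ between the two settings, and the plan itself treats the entry groups as not comparable.

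Taken literally, the BICLA test compares all voclosporin participants with all controls, whatever their Stage 2 arm. The other two tests are repeats of stratified Stage 2 tests. Sections 13.4.2 and 13.4.3 do not name those strata, and the hypotheses in Section 13.6 are indexed by the seven immunologic subgroups. A literal repeat would therefore not bring in Stage 2 arm.

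The stake is interpretation. An effect present only after MMF failure would be diluted by the larger placebo-origin group. An effect present only when both drugs are started together could be read as rescue of MMF non-responders.

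**Working it through.** **Inputs.** Stage 2 size and allocation, Section 13.7: "A study design with 120 participants randomized 1:1 to placebo or MMF", so 60 per arm. Expected Stage 3 entry, same section: at least 80% of the placebo arm and about 60% of the MMF arm. Re-randomization is 1:1.

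**Reproducing the plan's figures.** 0.80 × 60 = 48 and 0.60 × 60 = 36. Halved, these give 24 and 18 per cell, matching the four-group table in 13.7.

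**Share from each Stage 2 arm.** 48/(48 + 36) = 48/84 = 57% from placebo and 36/84 = 43% from MMF. If instead every Stage 2 failure entered Stage 3 under the survival ranges in 13.7 (placebo 10–15%, MMF 35–50%), entrants would be 51–54 from placebo and 30–39 from MMF. The placebo share is then 51/90 = 57% to 54/84 = 64%.

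**What an overall comparison estimates.** With 1:1 allocation within Stage 2 arm, the expected overall difference is (36/84) × effect after MMF failure + (48/84) × effect after placebo failure. The documents give no Stage 3 effect size, so the rates below are assumptions.

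- 30 points after MMF failure, none after placebo failure: 0.30 × 36/84 = 12.9 points overall.
- None after MMF failure, 30 points after placebo failure: 0.30 × 48/84 = 17.1 points overall, with no benefit in MMF failures.
- 20 points in both: 20 points overall.

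**Power under assumed rates.** Z-test with pooled variance, binomial enumeration, 2-sided 0.10 (the plan's threshold for a notable finding):

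| Assumed response (control → voclosporin) | Overall, 42 vs 42 | MMF-origin, 18 vs 18 | Placebo-origin, 24 vs 24 |
|---|---|---|---|
| 15→45% after MMF; 40→40% after placebo | 33% | 65% | no effect |
| 15→35% after MMF; 40→60% after placebo | 59% | 40% | 42% |

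In the first row, a Cochran-Mantel-Haenszel test stratified by Stage 2 arm also has about 33% power (simulation). Stratifying the overall test does not recover the MMF-failure effect; estimates within each arm are needed. With Fisher's exact test at 0.10, power for 15% vs 45% at 18 per arm is 51%.

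**Precision within strata.** Approximate 95% half-width = 1.96 × √[p₁(1−p₁)/n + p₂(1−p₂)/n].

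- MMF-origin, 15% vs 45%, n = 18: 1.96 × √(0.375/18) = 28 points.
- Placebo-origin, 40% vs 60%, n = 24: 1.96 × √(0.48/24) = 28 points.
- Interaction (difference between the two effects): 1.96 × √(0.375/18 + 0.48/24) = 40 points.

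**The case against.** The strongest reply is that this is silence and not a decision to pool. The repeated primary and log-rank tests are stratified tests, re-randomization is stratified by Stage 2 arm, and 13.7 foresees four groups, so a sympathetic analyst might supply the right strata. That stands for those two tests, where the fault is that the strata are not named. It does not cover BICLA, because Fisher's test has no strata. Nor does it supply a test for the four groups.

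Second, Stage 3 is exploratory and makes no power claim, and Section 2.1.2 poses only a gene-expression question. This limits the weight of the point. But the clinical endpoints are listed as secondary in Section 3.3.1, p-values will be printed, and mechanistic response is itself defined by BICLA.

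Third, pooling can gain power. If the benefit is similar in both groups, the overall test does better (59% against 40% and 42% above). This stands, and is why an overall stratified test should be kept beside the within-arm estimates.

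Stronger readings are tempting but not supported:

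- A reader might infer that over half of those compared never took MMF. All Stage 3 participants take MMF, and exclusion criterion 12 bars earlier use only within one year of randomization. What holds is that they received placebo, not MMF, in Stage 2.
- A reader might infer that the overall comparison is biased. Randomization is 1:1 within Stage 2 arm, so it is an unbiased average; the non-comparability in 13.4.6 is between entry groups, not between voclosporin arms.
- A reader might add that many MMF failures are not true non-responders, since Section 1.2.2 says "The earliest flares may start within a month, indicating that sufficient steroid dose was likely not given during the withdrawal phase". That remark concerns the first month. Under the hazards in 13.7, 17–29% of MMF failures fall by Week 4; the larger 45–72% is the share before Week 12, which the remark does not address. Splitting about 18 per arm further would leave cells too small to interpret.

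**Conclusion.** The point holds as a gap in specification with a practical consequence: no clinical analysis stated in the plan isolates the effect of voclosporin in people who failed on MMF, and the BICLA test as written merges them with a larger placebo-origin group (57% on the plan's figures, up to 64% under its survival assumptions). The overall comparison is valid as an average but does not by itself answer either question in 1.2.3.

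The size of the dilution depends on how the effect differs between groups, which the documents do not say. It runs from none (equal effects) to 30 points appearing as 13 if the effect is confined to MMF failures. The 33% against 65% power contrast belongs to that extreme case and reverses when effects are similar. Since Stage 3 is declared supportive, this is an inexpensive improvement worth making, not a threat to the trial's primary result.

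**What to change.** In 13.4.5 and the SAP:

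- Estimate each Stage 3 clinical endpoint (BICLA, treatment failure, time to failure) within each Stage 2 arm, with a confidence interval: about 18 vs 18 and 24 vs 24.
- Base any statement about adding voclosporin after MMF failure on the MMF-origin stratum only.
- Stratify any overall voclosporin test by the Stage 3 randomization strata: Cochran-Mantel-Haenszel in place of Fisher for BICLA, a stratified log-rank test, and a stratified landmark test at Week 24.
- Report a voclosporin-by-Stage-2-arm interaction estimate with its interval.

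The cost is wording only; no data, visits or participants are added. The downside is imprecision, about ±28 points within a stratum and ±40 for the interaction under the rates assumed above. The plan should say in advance that these estimates are descriptive.
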